### 9. PRIOR AND CONCOMITANT MEDICATION

Prior and concomitant medications in addition to the study drug will be summarized descriptively using the safety and the ITT populations. Prior and concomitant medications will be coded using the World Health Organization (WHO) Drug Dictionary.

### 10. EFFICACY ANALYSES

Unless otherwise specified, all efficacy analyses will be using the defined ITT population.

#### 10.1. PRIMARY EFFICACY ANALYSIS

• The time to and percent of patients who attain the initial pre-specified SBP target range within the first 30 minutes of study drug initiation.

The time to attain the initial pre-specified SBP target range is in minutes and is the duration between the initiation of study medication and the time a patient first achieves the initial pre-specified target SBP range (TBPR) during the first 30 minutes of clevidipine infusion. The time will be summarized using descriptive statistics and the Kaplan-Meier curve. The estimated median time with its two-tailed 95% confidence interval (CI) [Simon and Lee, 1982] will be presented. If a patient does not reach TBPR within 30 minutes from the initial treatment with study medication, or another antihypertensive agent is administered, the patient will be considered censored at 30 minutes or the time when another antihypertensive agent is given, whichever comes first.

The percentage of patients achieving the TBPR will be calculated using the number of ITT patients achieving TBPR divided by the number of ITT patients, and multiplied by 100. Two-tailed 95% CIs will be computed for these percentages.

• The dose to attain the initial pre-specified target SBP range (minimum of 20 mmHg and a maximum of 40 mmHg apart) during the first 30 minutes of clevidipine infusion.

The dose to attain the initial pre-specified target SBP consists of the infusion rate  $(\mu g/kg/min)$ , total dose (mg) infused, and number of titrations made when TBPR is reached.

The summary statistics on infusion rate, total dose infused, and number of titrations made when TBPR is reached will be presented.

All the aforementioned analyses will be performed using the ITT population and also for data exploration using the safety population.

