5.2.2. Prohibited Concomitant Medications

The following medications are prohibited and should not be administered to the patient within 2 hours prior to receiving treatment with clevidipine:

- 1. Methylphenidate
- 2. Aripiprazole and other atypical anti-psychotics
- 3. Calcium channel blockers
- 4. All other antihypertensive agents used for BP control

This is a study of an IV antihypertensive agent in a pediatric surgical population. Use of nonstudy drug medications and treatment procedures that affect the BP are discouraged during study drug administration, especially during the initial 30-minute period of study drug treatment. It is anticipated that an alternative antihypertensive agent(s) as rescue therapy will only be used if the study drug does not adequately lower BP. If a rescue therapy is used, it must be recorded in the eCRF, and the reason for such use must be documented.

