5.2.3. Permitted Concomitant Medication(s)

- 1. Oral contraceptives will be permitted during the study for females of child-bearing potential
- 2. Beta-adrenergic blockers used specifically for reflex tachycardia
- 3. Ace inhibitors for volume overload

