10.3.2. Efficacy Analysis

10.3.2.1. Primary Efficacy Endpoints

The primary efficacy endpoints of this trial are:

- Median time and dose to attain the initial prespecified target SBP range (minimum of 20 mmHg and a maximum of 40 mmHg apart) during the first 30 minutes of clevidipine infusion
- Percentage of patients achieving the initial prespecified target SBP range during the first 30 minutes of clevidipine infusion

Median time is the median of the time in minutes between the initiation of study medication and time the patient first achieves the initial prespecified target SBP range (TBPR) during the first 30 minutes of clevidipine infusion. The median time will be summarized using the Kaplan-Meier method. Median time will be estimated with a two-tailed 95% confidence interval. If patients do not reach TBPR within 30 minutes from the initial treatment with study medication, or another intravenous antihypertensive agent is administered, the patient will be considered censored at 30 minutes or the time when another intravenous antihypertensive agent is given, whichever comes first.

The percentage of patients achieving TBPR will be calculated using the number of ITT patients achieving the endpoint divided by the total number of ITT patients, and multiplied by 100.

Number and percent of patients achieving TBPR during the first 30 minutes along with the calculated 95% confidence interval will be presented.

Analysis of the infusion rate, total dose infused, and total volume infused at the time of first achieving TBPR during the first 30 minutes will be summarized descriptively.

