Cohort 1 (ages 12 to less than 18 years) will receive an initial weight based dose of ; this rate will be maintained for the first 1.5 minutes. If the target SBP range is not achieved within 1.5 minutes, the clevidipine infusion rate may be up-titrated incrementally per the protocol dosing, progressing to up to the maximum dose of every 1.5 minutes until a SBP within the pre-specified target range is reached. The initial dose and the subsequent up-titration doses for Cohorts 2, 3 and 4 will be determined after an interim analysis of data from the preceding cohort. As the blood pressure approaches the desired range, dosing may be increased by less than doubling, and the time between dose adjustments may be

lengthened to greater than 1.5 minutes. If the target SBP range is achieved at any of the titration doses, that rate may be maintained for up to 96 hours to maintain the BP, or titrated up or down as necessary to maintain SBP within the target range. Clevidipine infusion may be terminated at any time for safety reasons.

During the initial 30 minutes of the treatment period, clevidipine should be administered continuously as monotherapy. The use of an alternative IV antihypertensive agent is discouraged and should be limited to situations where it is medically necessary to maintain patient safety. If the desired BP control effect is not attained using the maximum dose of clevidipine, rescue therapy with the use of an alternative IV antihypertensive agent should be implemented.

After the first 30-minute treatment period, it may be necessary to alter the desired SBP target range over the course of the remaining treatment period. Any changes in the target range will be captured in the electronic case report form (eCRF).

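### Censoring time to target at rescue is informative: it overstates the later Kaplan-Meier curve, and shortens the median only where response is poor and rescue early

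*SAP*

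**What the plan says.** Median time to the initial target SBP range is a primary efficacy endpoint. SAP 10.1 states: "The time will be summarized using descriptive statistics and the Kaplan-Meier curve", with an estimated median and its 95% CI. For a patient who does not reach target within 30 minutes, or who is given another agent, "the patient will be considered censored at 30 minutes or the time when another antihypertensive agent is given, whichever comes first". Protocol 10.3.2.1 has the same rule with a narrower trigger: "the patient will be considered censored at 30 minutes or the time when another intravenous antihypertensive agent is given, whichever comes first".

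On why another agent is given, SAP 1.1 reads "If the desired BP control effect is not attained using the maximum dose of clevidipine, rescue therapy" is to be implemented, and Protocol 5.2.2 expects that alternative agents "as rescue therapy will only be used if the study drug does not adequately lower BP". SAP 1.1 adds that an alternative IV agent "should be limited to situations where it is medically necessary to maintain patient safety". Protocol 6.5.2 foresees an added agent inside the first 30 minutes, since it schedules PK Sample 5 for that case.

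The companion primary endpoint, the percentage attaining target, keeps every ITT patient in the denominator (SAP 10.1). Neither document treats rescue as a competing event or as non-attainment in the time analysis, and neither plans a sensitivity analysis for it.

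**The concern.** Kaplan-Meier treats a censored patient as having the same later chance of attaining target as the patients still at risk. A patient rescued because clevidipine did not work does not have that chance on clevidipine. Taking such patients out of the risk set removes known failures from the denominator, so the curve rises too far from the first rescue onward. Censoring at 30 minutes is administrative and harmless; the problem is the earlier censoring at rescue.

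The study is single-arm and descriptive, so these estimates are its result. The curve can suggest a higher attainment rate than the ITT percentage. In an age cohort of 20 that responds poorly, a finite median can be reported although fewer than half attained. The overstatement grows as the drug performs worse.

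The two triggers also differ. Without the protocol's restriction to intravenous agents, the SAP wording could censor at a permitted drug given for another reason, such as "Beta-adrenergic blockers used specifically for reflex tachycardia" (Protocol 5.2.3).

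**Working it through.** **The plan's own figures.** SAP 16 gives the 95% CI half-width for the percentage with n = 80. Using 1.96·√(p(1−p)/n): at p = 0.90, 1.96·√(0.09/80) = 6.57%; at p = 0.85, 1.96·√(0.1275/80) = 7.82%. Both match the stated ±6.6% and ±7.8%. The planning range for attainment is therefore 85-90%.

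**Formula.** Suppose A1 patients attain before the rescues, R are then rescued, A2 attain later and U do neither, with N in total.

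- Planned censoring: curve at 30 min = 1 − [(N − A1)/N]·[U/(N − A1 − R)].
- Rescued patients held as non-attainers to 30 min: curve = (A1 + A2)/N. This equals the cumulative incidence with rescue as a competing event.

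**Hand example at the planned rate.** N = 80 is from the SAP; A1 = 44 is assumed.

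| Attain | Rescued early | Planned curve at 30 min | Held as non-attainers |
|---|---|---|---|
| 72 (90%) | 0 of 8 | 1 − (36/80)(8/36) = 90.0% | 90% |
| 72 (90%) | 4 of 8 | 1 − (36/80)(4/32) = 94.4% | 90% |
| 72 (90%) | 8 of 8 | 1 − (36/80)(0/28) = 100% | 90% |
| 68 (85%) | 6 of 12 | 1 − (36/80)(6/30) = 91.0% | 85% |

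In every row the curve passes 50% before any rescue (44 of 80 have attained), so the median is the same under both methods.

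**Simulation near the planned rate.** All inputs other than n = 80 and the 1.5-minute reading grid are assumptions: attainers' times lognormal, median 7 min, log-SD 0.7; rescue at 7.5-15 min. About 2% of the lognormal lies beyond 30 min, so 10-15% non-attainers gives 83-88% attaining rather than 85-90%.

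| Non-attainers rescued early | Planned curve at 30 min | Attaining |
|---|---|---|
| none | no bias | 83-88% |
| half | about 89-92% | 83-88% |
| all | about 97% | 83-88% |

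With log-SD varied from 0.5 to 0.9 and all non-attainers rescued, the overstatement is 8-15 percentage points. At log-SD 0.7 the two medians were identical in at least 99% of simulated trials. With a slower attainer median of 10 min and all rescued at 6-15 min, the mean median moved from 11.8 to 12.0 min (90% attaining) and from 12.6 to 13.1 min (85%).

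**Poor response, early rescue.** With 45% non-attainers, all rescued at 7.5-15 min, about 54% attain but the planned curve reads about 95%. The mean median is about 13 min under censoring (about 14 if rescue times are rounded up to the next reading) against about 17 min.

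**A cohort of 20 (assumed counts).** Five attain, six are then rescued at 8-10 min, four attain later, five do neither.

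- Planned: the curve at 30 min is 1 − (15/20)(5/9) = 58.3%. The proportion not yet attained is (15/20)(7/9) = 0.583 after the second late attainment, (15/20)(6/9) = 0.50 after the third and 0.417 after the fourth. A finite median is therefore reported: 18 min if the third late attainment falls there.
- Held as non-attainers: 9/20 = 45%, and the median is not reached.

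These comparisons count as attainers only patients who reach target before any rescue. SAP 10.1 does not say whether reaching target after rescue counts in the percentage.

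**The case against.** The strongest reply is that the planned summary of time is the median, and at the attainment the plan assumes the median does not move. That stands. A reader might infer that censoring at rescue generally shortens the median; it does not when half the patients attain before the rescues.

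A reader might also take the largest gaps, such as 97% against 79% with 20% non-attainers, as the expected error. Those require every non-attainer to be rescued early. The documents give no rescue rate or time, and they lean toward little early rescue: alternative agents are discouraged in the first 30 minutes, and loss of 30-minute monotherapy is a major deviation (Protocol 12.3). With half rescued, the same 20% scenario gives about 84-86% against 78-80%.

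Nor do the documents support saying that two figures in one table will contradict each other. The SAP plans a curve, a median and a separate percentage; it does not plan to tabulate the curve's 30-minute value. The percentage itself carries no censoring bias, and rescue and the reasons for not completing monotherapy are reported elsewhere (SAP 10.2.4 and 8).

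It can be added that censoring at rescue suits the interest in monotherapy (Protocol 7.2.2), and that some agents may be given for safety rather than failure. Neither removes the dependence: Kaplan-Meier still needs rescued patients to resemble those left at risk, and the plan's main ground for rescue says that they do not.

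**Conclusion.** The concern holds in limited form. As written, the rule is informative censoring, and it overstates the Kaplan-Meier curve after the first rescue. Near the planned attainment the overstatement at 30 minutes is roughly 4 to 6 points if half of the non-attainers are rescued early (92 against 88; 89 against 83), and 8 to 15 points if all are. The second range exceeds the ±6.6-7.8% precision on which the sample size rests. The median is essentially unaffected there. It is materially understated only in a poorly responding cohort with early rescue, where a finite median may also be reported although fewer than half attained.

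The direction follows from the documents whenever rescue before attainment reflects lack of effect. The sizes rest on assumed rescue fractions, rescue times and attainment times. The point merits correction before analysis; it does not undermine the primary percentage.

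**What to change.** In SAP 10.1 and Protocol 10.3.2.1:

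1. Keep patients who receive rescue before attainment in the risk set as non-attainers to 30 minutes, or equivalently use cumulative incidence with rescue as a competing event. Take the median and its CI from that curve, and report the median as not reached if fewer than 50% attain.
2. Keep the rescue-censored curve as a supportive analysis.
3. Reconcile the trigger wording (any antihypertensive agent in the SAP, intravenous agents only in the protocol), and define rescue for this analysis so that permitted agents given for other reasons are not counted.
4. If the descriptive statistics of time are restricted to attainers, label them as attainers only. The SAP does not say which patients they cover.

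The cost is a few sentences and standard software, using data already collected and with no change to patient management. The downside is that the reported curve will be lower wherever early rescue occurs, and in a poorly responding cohort the median may be longer or not reached.

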10.3.2.2. Secondary Efficacy Endpoints

The secondary efficacy endpoints are:

• The percentage of patients who reach the initial prespecified target SBP range without falling below the lower limit of the prespecified target range during the first 30 minutes of clevidipine infusion

- The percentage of patients in whom the SBP falls below the lower limit of the pre specified target range at any time during the first 30 minutes and at any time during the entire study drug treatment period
- The percentage of patients in whom the SBP is within target range at each hour after the first 30 minute of clevidipine infusion
- The percentage of patients who require rescue therapy (i.e., receive any alternative IV antihypertensive drug) at any time during study drug treatment period or discontinuation due to adverse events.

The percentage of patients reaching each endpoint above will be calculated for overall and within each cohort using the number of ITT patients achieving the endpoint divided by the number of total ITT patients, and multiplied by 100.

Number and percent of patients achieving each endpoint during the first 30 minutes along with the calculated 95% confidence interval will be presented.

- Percent change in SBP from baseline at each time point during the 30 minutes of clevidipine infusion
- Percent change from baseline in SBP at each hour after the first 30 minutes of clevidipine infusion up to the cessation of infusion
- Percent change from baseline in SBP over the first 12 hours post study drug termination
- Percent change from baseline in heart rate during the first 30 minutes of clevidipine infusion and the rest of the treatment period

Percent change from baseline at each time point specified in above endpoints will be calculated for each ITT patient.

Descriptive statistics will be presented for overall and by cohort.

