### 3.2. INTENT-TO-TREAT (ITT) POPULATION

The ITT population consists of all patients who are dosed with any study drug and have baseline and at least one post-baseline SBP measurement. This will be the primary population used for the efficacy analyses.

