## 10.2.4. The percentage of patients who require rescue therapy (i.e. receive any alternative IV antihypertensive drug) at any time during study drug treatment period or discontinuation due to adverse events

The percentage of patients achieving this endpoint will be calculated using the number of patients achieving the endpoint divided by total number of patients, and multiplied by 100. Two-tailed 95% CIs will be computed for these percentages.

Number and percent of patients achieving the endpoints along with the calculated 95% CI will be presented.

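### The primary percentage reaching target SBP has no rescue condition, while time-to-target is censored at rescue, so a patient first in range only after rescue can be a success in one and censored in the other

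*SAP*

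**What the plan says.** SAP 10.1 defines three primary efficacy summaries: time to the prespecified SBP range (TBPR), percentage attaining it, and dose at attainment.

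- **Time.** If TBPR is not reached by 30 minutes "or another antihypertensive agent is administered, the patient will be considered censored at 30 minutes or the time when another antihypertensive agent is given", whichever is earlier. Protocol 10.3.2.1 has the same rule, limited to intravenous agents: "the patient will be considered censored at 30 minutes or the time when another intravenous antihypertensive agent is given, whichever comes first".
- **Percentage.** In the SAP it is "calculated using the number of ITT patients achieving TBPR divided by the number of ITT patients"; in Protocol 10.3.2.1 it is "calculated using the number of ITT patients achieving the endpoint divided by the total number of ITT patients". Neither sentence mentions rescue.
- **Dose.** The SAP summarises "infusion rate, total dose infused, and number of titrations made when TBPR is reached", again without a rescue condition.

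The ITT population is everyone "dosed with any study drug and have baseline and at least one post-baseline SBP measurement", so rescue removes nobody. Rescue is a separate secondary endpoint in Protocol 10.3.2.2 and SAP 10.2.4, defined as receiving any alternative IV antihypertensive and reported together with discontinuation for adverse events. SAP 18, which lists changes from the protocol, adds no rule on this point.

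**The concern.** The rescue rule is attached to one variable only. A patient given an alternative agent at minute 12 and first in range at minute 18 is censored at 12 in the time analysis. The percentage formula, followed literally, counts the same patient as attaining. Protocol 7.2.2 says concomitant BP medication is monitored to establish efficacy as monotherapy, so counting that patient works against the stated aim, and the error can go only upward.

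Three other results use the same attainment idea:

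- SAP 10.2.1 (attaining without falling below the lower limit) has the same gap.
- The sponsor's precision review after each cohort (SAP 15) is based on the count reaching TBPR.
- The dose-to-target summary would record a clevidipine rate that did not by itself produce the response. Under Protocol 6.5.2, clevidipine may be reduced or stopped once the other agent has started.

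The time analysis has a further weakness. Where rescue follows failure at the maximum dose, censoring at rescue is informative and pushes the Kaplan-Meier attainment curve up.

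**Working it through.** **Can the case arise?** Yes.

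1. SAP 1.1 and Protocol 6.5.2 foresee rescue when the maximum dose does not achieve control.
2. Protocol 6.5.2 provides for PK Sample 5 when an additional agent is needed before minute 30, with BP still read every 1.5 minutes afterwards. A first in-range reading after rescue would be captured.
3. SAP 1.1 and Protocol 6.5.2 let rescued patients continue. Protocol 3.1 words this for rescue after the first 30 minutes; these passages need reconciling. ITT membership does not depend on the answer.

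**The plan's own precision.** SAP 16 gives ±6.6 points at 90% and ±7.8 at 85%, n = 80. With half-width = 1.96 × √(p(1−p)/n):

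- p = 0.90, n = 80: 6.57 points
- p = 0.85, n = 80: 7.82 points

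Both reproduce.

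**Limits on the percentage.** The number rescued before target is not given. The most that could be added is the number not attaining on clevidipine.

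| Attaining on clevidipine | n | Non-attainers | Reported value could be | Per patient |
|---|---|---|---|---|
| 85% | 80 | 80 × 0.15 = 12 | 85% to 100% | 1.25 points |
| 90% | 80 | 80 × 0.10 = 8 | 90% to 100% | 1.25 points |
| 85% | 20 | 20 × 0.15 = 3 | 85% to 100% | 5 points |
| 90% | 20 | 20 × 0.10 = 2 | 90% to 100% | 5 points |

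The upper ends are limits, not forecasts. As an illustration, four such patients turn 68/80 (85%) into 72/80 (90%), a shift of 5 points against a planned half-width of 6.6.

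**Cohort precision review.** One patient turns 17/20 (85%, ±15.6) into 18/20 (90%, ±13.1). The n for ±6.6 points is 1.96² × p(1−p)/0.066²:

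- p = 0.85: 112.4, so 113
- p = 0.90: 79.4, so 80

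SAP 15 sets no numeric threshold and leaves the decision to clinical judgement, so no changed decision is shown.

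**Kaplan-Meier curve at 30 minutes.** Let G be the fraction attained before rescue, r the fraction rescued (all at one time), and u = 1 − p − r the fraction neither attaining nor rescued. Attainment on the curve is 1 − (1−G)·u/(1−G−r). With true p = 0.85:

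| r | G = 0.5 | G = 0.7 | G = 0.8 |
|---|---|---|---|
| 0.05 | 88.9% | 88.0% | 86.7% |
| 0.10 | 93.75% | 92.5% | 90.0% |

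The curve is displayed; the endpoint is the median.

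**Median.** If half attain before the first rescue, nothing changes. If G < 0.5, the Kaplan-Meier median falls where crude attainment is G + (1−G−r)(1 − 0.5/(1−G)). The extreme is G = 0 with every non-attainer rescued:

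- 85% plan: 0.85 × 0.5 = 42.5% attained
- 90% plan: 0.90 × 0.5 = 45% attained

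A simulation compared the current rule with censoring at 30 minutes. Its inputs are assumptions, not document figures: lognormal attainment times (σ = 0.5, within 30 minutes) rounded up to the next 1.5-minute reading, rescue times uniform over 6 to 15 minutes, 4 to 12 of 80 rescued at 85% attainment or 4 to 8 at 90%, and 600 trials per setting. At n = 80:

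| Median attainment time | Trials with a different median |
|---|---|
| 4 or 6 min | none |
| 8 min | 0.3% to 6% |
| 12 min | 6% to 36% |

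The change was one reading (1.5 minutes), occasionally two.

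**The case against.** The strongest reply is that one event flag is implied. Time and percentage share a bullet in SAP 10.1, TBPR attainment is defined once, and a programmer could derive a single indicator that respects the censoring. That is a fair reading, so the defect is an unstated rule whose literal formula gives the unwanted answer. Neither document writes the single-flag rule, and the censoring sentence concerns time only.

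The wording also ties attainment to the clevidipine infusion, so a reading after clevidipine has been stopped arguably does not count. That helps only in part: patients whose infusion is merely reduced are not covered, and the bullet itself counts from study drug initiation.

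The consequence may be small. The study is descriptive with no formal testing, other agents are discouraged in the first 30 minutes, and loss of monotherapy in that window is a major protocol deviation (Protocol 12.3). Affected patients would be visible in the deviation table (SAP 7), the monotherapy yes/no item with reason (SAP 8), the rescue endpoint (SAP 10.2.4), individual SBP graphs and the listings. All of this stands and limits the weight of the point, but none of it changes the primary percentage.

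Finally, censoring at the agent is prespecified in the protocol, and the median is usually robust to it. That is a reason to keep the rule as a sensitivity analysis. Protocol 5.2.2 anticipates rescue only where study drug does not lower BP adequately, which makes informative censoring more likely, although SAP 1.1 also allows another agent on safety grounds and no split is given.

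**Conclusion.** The concern holds. The percentage attaining target is a primary endpoint with no rescue condition, beside a time endpoint that has one, and the plan's own procedures allow the patient who exposes the difference. The bias runs one way, upward, by 1.25 points per patient at n = 80 and 5 points in a cohort of 20. The limit is 12 patients of 80 at 85% attainment and 8 at 90%. The actual size is unknown and may be nil, because the documents give no rescue rate. The displayed curve can overstate attainment by about 2 to 9 points at the assumed rescue fractions of 5% and 10%. The median moves only if rescue is frequent and precedes 50% attainment.

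A smaller point also stands. The SAP censors at any other antihypertensive, the protocol only at an intravenous one. SAP 18 does not list the change, and neither text says whether the agents permitted in Protocol 5.2.3 count. This should be fixed before analysis; it does not invalidate the design.

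**What to change.** In SAP 10.1:

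1. Define attainment once: the first in-range SBP within 30 minutes must precede any alternative IV antihypertensive, whatever its eCRF label. Otherwise the patient is a non-attainer and stays in the denominator. This matches the existing rescue definition ("i.e., receive any alternative IV antihypertensive drug"). Use the same flag for the percentage, SAP 10.2.1, the dose-to-target summary and the SAP 15 count.
2. In the time analysis, censor patients given such an agent before target at 30 minutes. The Simon and Lee interval still applies, and the curve at 30 minutes then equals the percentage if nobody else is censored earlier. Keep censoring at the time of the agent as a sensitivity analysis. Report the median as not reached if fewer than 50% attain.
3. Align the SAP and protocol wording on which agents trigger the rule, and state how those permitted in Protocol 5.2.3 are handled in the analysis, showing results both ways if any are given before target. List any remaining departure in SAP 18.

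Separately, reconcile the passages on continuation after rescue (Protocol 3.1 against Protocol 6.5.2 and SAP 1.1).

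The cost is a few sentences and a few lines of programming on data already collected. Attainment figures may come out slightly less favourable.
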